2.15.2 Sample Size Rationale

The primary outcome will be the development of the practicality of the device. Based on the need for data collected from this study, it was determined that a total of 20 subjects will be required, including departures.

2.15.3 Patient Populations

Interim results may be collected and reported. All data will be analyzed at the end of the study. The primary analysis will be performed by the intention-to-treat approach. Everyone who begins the treatment is part of the study whether he or she completes the study or not. Additional perprotocol analysis may also be performed on subjects who complete the entire clinical trial according to the protocol. The most appropriate method of handling missing values will be chosen based on the individual trial goals, endpoints and context.

The analysis of demographic, medical history, and efficacy variables will be based on all patients who are randomized and receive at least one treatment. The analysis of safety data will be based on all patients who are randomized, receive at least one treatment, and have at least some safety data.

2.15.4 Analysis of Demographic and Medical History Variables

Summaries will be prepared for all important demographic and medical history variables. For quantitative variables summaries will include the sample size, mean, median, standard deviation, minimum, and maximum. For these variables the treatment groups will be compared using either a t-test or a Wilcoxon Rank Sum test, as appropriate. For categorical variables the summaries will include the sample size and the number and percent of patients for each outcome. For these variables the treatment groups will be compared using Fisher's Exact test. Statistical significance will be declared if the two-sided p-value is < 0.05.

2.15.5 Analysis of Efficacy Variables

The primary efficacy variable is the change from baseline to visit 7 (60 days post last treatment, +/- 30 days) with respect to the indication being treated as evaluated by physician grading with CGAIS. Baseline is defined as the last assessment prior to the first treatment. The change from baseline to visit 13 will be analyzed using a Mixed Model Repeated Measures Analysis of Variance. A pairwise treatment group comparison at visit 7 will be performed using the results of this analysis. If a patient has no post-baseline assessment of the primary efficacy variable the patient data will be excluded from the statistical analysis of the improvement. Statistical

significance with respect to the treatment group comparison at visit 7 will be declared if the two-sided p-value is < 0.05. For each treatment group summaries will be prepared for both the observed assessment and the change from baseline. Subject satisfaction results from Visits 12 and 13 will also be included in the summary. The summaries will include the sample size, mean, median, standard deviation, minimum, and maximum. Categorical variables will also include a summary which will include the number and percent of patients for each outcome. The statistical significance of the mean change from baseline for each treatment group will be determined using a student's paired t-test.

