1.2 Objectives

- 1. Primary Objectives:
 - To assess the safety of the study devices through the collection of side effects throughout the study.
 - To assess efficacy by blinded evaluation of photography.
- 2. Secondary Objectives:
 - To assess of efficacy of the study device through Investigator and subject questionnaires.
 - To assess the ease of use of the new device.

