2.2 Protocol Study Design

This is a prospective, open label, single-center clinical study to collect safety and efficacy data on the Elite iQ workstation.

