2.13 Evaluation Methods

Photographs:

Photographs will be taken at all visits and will be used to assess safety and efficacy of treatment.

Treatment Discomfort/Pain Evaluation:

Subjects will be asked to report the general level of treatment discomfort on a scale of 0 (none) to 10 (maximum intolerable pain) using the universal pain assessment tool (Appendix B)

Subject Questionnaire:

The subject will be asked their level of satisfaction using a 6-point Likert scale that ranges from "extremely satisfied" to "extremely unsatisfied."

Subject Satisfaction		
Rating	Description	
6	Extremely Satisfied	
5	Satisfied	
4	Slightly Satisfied	
3	Slightly Unsatisfied	
2	Dissatisfied	
1	Extremely Unsatisfied	

Physician Questionnaire:

The Clinical Global Aesthetic Improvement Scale (CGAIS) ranging from "worse" to "very much improved" will be used to judge the improvement as seen by the treating Investigator.

Global Aesthetic Improvement Scale Assessment		
Rating	Description	
1	Very Much Improved- Optimal cosmetic result in this subject	
2	Much Improved- Marked improvement in appearance form the initial	
condition, but not completely optimal for this subject.		
3	Improved- Obvious improvement in appearance from initial condition, but a re-treatment is indicated.	
4	No Change- The appearance is essentially the same as the original condition.	
5	Worse- The appearance is worse than the original condition.	

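### The primary efficacy objective is a blinded reading of photographs, but the analysis section makes the treating investigator's open-label CGAIS grade primary and never analyses the blinded reading

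*Combined protocol and SAP*

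**What the plan says.** - **Section 1.2, primary objectives.** There are two: safety, and "To assess efficacy by blinded evaluation of photography".
- **Section 1.2, secondary objectives.** These include "To assess of efficacy of the study device through Investigator and subject questionnaires".
- **Section 2.2.** "This is a prospective, open label, single-center clinical study".
- **Section 2.13.** The CGAIS is the physician questionnaire and "will be used to judge the improvement as seen by the treating Investigator". It runs from 1 (best) to 5 (worse). Grade 4 means "The appearance is essentially the same as the original condition". Photographs are said to serve the assessment of safety and efficacy, but no reading scale, number of readers or response definition is given.
- **Section 2.15.5.** The primary efficacy variable is the change to Visit 7 "with respect to the indication being treated as evaluated by physician grading with CGAIS". Two analyses follow: "The change from baseline to visit 13 will be analyzed using a Mixed Model Repeated Measures Analysis of Variance" and "A pairwise treatment group comparison at visit 7 will be performed using the results of this analysis". The section adds a paired t-test of mean change within each treatment group, and a summary of subject satisfaction at Visits 12 and 13.
- **Section 2.15.1.** Under secondary objectives, scale scores such as the GAIS are tested against a no-change average of 4.
- **Section 3.2.** Photographs that are a primary objective must be read by blinded evaluators from outside the study. Investigator assessment of improvement, if collected, is not to be listed as an objective.

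**The concern.** The objectives and the analysis section name different primary efficacy measures, and they differ in who does the grading. Section 1.2 relies on readers who are blinded. Section 2.15.5 relies on the person who gave the treatment and knows it was given.

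Two things are at stake. First, the objective that the protocol ranks highest for efficacy has no score, test or summary. The scale, the readers and the test could therefore be settled after the images have been seen. Second, the measure presented as primary would be the one that 1.2 ranks as secondary and that 3.2, in its discussion of bias, seeks to keep out of the objectives.

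**Working it through.** **Step 1: the texts side by side.** The plan gives no effect size, variance, response rate or power for either measure, so it has no figure to reproduce.

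| Section | What is primary, or how efficacy is judged |
|---|---|
| 1.2 | Blinded photograph evaluation; investigator questionnaire is secondary |
| 2.15.1 | Study success rests on parameters and side effects; the GAIS test sits under secondary objectives |
| 2.15.2 | Primary outcome is the practicality of the device |
| 2.15.5 | Physician CGAIS |
| 2.15.1 to 2.15.6 | No mention of photographs or blinded evaluators |

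**Step 2: can the text be read consistently?**
- Physician grading in 2.15.5 might mean a blinded physician reading images. Section 2.13 rules this out by giving the CGAIS to the treating investigator.
- The wording in 2.15.1 about assessments in general might cover the blinded reading. That sentence is confined to secondary objectives.

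**Step 3: can the tests in 2.15.5 be run?**
- The schedule in 2.12 ends at Visit 7, so there is no visit 13 for the mixed model and no Visit 12 or 13 for the satisfaction summary.
- The design describes no second group, so there is no treatment-group comparison to make.
- The paired t-test has no observed baseline, because the CGAIS already grades change from the starting condition and is scheduled only at Visit 7. If every baseline is set to 4, then d = x − 4, the mean of d is the mean of x minus 4, and the SD of d equals the SD of x. So t = (mean of x − 4)/(SD/√n), which is the one-sample test in 2.15.1. The paired test works only in that form.

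**Step 4: what an unblinded grader could do (illustration only).** Assumptions: no true effect; each subject scores 3, 4 or 5 through grading error alone; two-sided one-sample t-test against 4 at 0.05; only significant results below 4 are counted; samples with no variance count as not significant. Probabilities come from exact trinomial enumeration. The column for 16 evaluable subjects is a further assumption.

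| Upgrades / downgrades | n = 20 | n = 16 |
|---|---|---|
| 10/10, 20/20, 30/30% | 0.02 to 0.03 | about 0.02 |
| 10/5% | 0.06 | 0.04 |
| 20/10, 30/10% | 0.11, 0.27 | 0.10, 0.23 |
| 20/5, 30/5% | 0.26, 0.49 | 0.20, 0.41 |
| 40/5% | 0.71 | not needed |

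The nominal rate in this direction is 0.025. Symmetric error gives no inflation. The rate rises when upgrades become more frequent and also when downgrades become rarer.

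**Step 5: could a blinded reading work with 20 subjects?** Take one possible test, picking the better image, as an exact two-sided binomial against 50%.
- n = 20: P(X ≥ 15 | 0.5) = 0.0207, doubled 0.041. With 14 correct the doubled value is 0.115, so 15 are needed.
- n = 16 (assumption): P(X ≥ 13 | 0.5) = 0.0106, doubled 0.021. With 12 correct it is 0.077, so 13 are needed.
- If a share g of pairs is distinguishable and the rest are guessed, the chance of a correct pick is (1 + g)/2.

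| g | Correct picks | Power, n = 20 | Power, n = 16 |
|---|---|---|---|
| 0.4 | 70% | 0.42 | 0.25 |
| 0.6 | 80% | 0.80 | 0.60 |
| 0.8 | 90% | 0.99 | 0.93 |

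These figures hold only if nothing but treatment differs between the two images. Section 2.6 sets a hair-growth period for the baseline photographs of hair-removal subjects, and no section sets one for Visit 7.

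**The case against.** The best case for leaving the plan alone is that this is a 20-subject, single-center study of a cleared device. Its success rule depends on parameters and side effects, and its sample size on practicality. That stands, and it confines the damage to the efficacy claim. It does not supply an analysis for a stated primary objective.

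Several stronger readings are tempting, and the documents do not support them:

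- **That the CGAIS is optional.** Section 2.9 says questionnaires may be done at follow-up. But 2.12 schedules the investigator questionnaire at Visit 7, and 2.13 states without qualification that the scale is used. This is an inconsistency to reconcile.
- **That 2.15.5 breaks the rule in 3.2 outright.** The rule limits what is listed as an objective, and 2.15.5 names an analysis variable. The literal conflict is with the secondary objective in 1.2. Section 2.15.5 goes against the intent of 3.2, not its letter.
- **That no CGAIS test is usable.** The one-sample test against 4 in 2.15.1 is usable, and the paired t-test reduces to it.
- **That the investigator's grades are known to be inflated.** No document gives the size or direction of grading error.
- **That missing data are ignored.** Section 2.15.5 excludes patients with no post-baseline assessment of the primary variable, and 2.15.3 calls for intention-to-treat while leaving the missing-data method open. The text exists, but it does not settle the matter.

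The visit 12/13 and group-comparison errors would exist whichever measure were primary. They belong here because they leave 2.15.5 without a sound analysis even of the variable it names.

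**Conclusion.** The concern holds and must be fixed before the efficacy data are analysed. Sections 1.2 and 2.15.5 name different primary efficacy measures. The one in 1.2 has no analysis, and the one in 2.15.5 is an open-label grade by the treating investigator. The mixed model, the group comparison and the Visit 12/13 summaries cannot be carried out in this single-group study.

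This conclusion rests on the text alone and needs no numerical assumption. Its reach is limited to the efficacy claim. The grading-error table shows what asymmetric error could do, but upward bias is plausible rather than demonstrated, and the severity does not depend on it.

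**What to change.** In section 2.15.5:

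1. Make the primary efficacy variable the blinded reading of baseline and Visit 7 photographs by the outside evaluators that 3.2 requires, with visit labels removed and image order randomised.
2. Define one score per subject, with a rule for combining several treatment areas, and one one-sample test against no change. The scale is the sponsor's choice, provided it works without knowing which image is baseline. Picking the better image is one example, but it discards the degree of improvement. A symmetric signed score tested against 0 is another.
3. State the number of readers, how disagreements are resolved, and how a missing Visit 7 photograph is counted, consistently with 2.15.3.
4. Delete the mixed model, the treatment-group comparison and the Visit 12/13 references. Keep the treating investigator's CGAIS as supportive, tested one-sample against 4, in place of the paired t-test.

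Elsewhere, reconcile the hair-growth condition of the baseline and Visit 7 photographs so that it neither reveals image order nor mimics an effect. Name the same primary efficacy endpoint in 1.2, 2.15.1, 2.15.2 and 2.15.5. Reconcile 1.2 with 3.2, and 2.9 with 2.12 and 2.13.

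**Cost.** A protocol amendment with IRB approval and a short written reading procedure. The photographs and the outside evaluators are already committed, so no visits or subjects are added. The blinded result may be less favourable than the investigator's grade, power is limited, and masking the readers does not replace a control group.

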2.9 Follow Up

- The study subjects are required to return to Investigator site for a follow up evaluation between 30 90 days post last treatment.
- Subject and Investigator questionnaires may be performed at these visits.
- Photographs will be taken, and adverse events will be documented at all follow up visits.
- Some subjects may have an incomplete response or no response by the end of the study. At the end of the study, treatments using an FDA approved/cleared treatment method may be discussed with the subject and obtained at the cost of the subject.

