2.12 Schedule of Visits and Procedures

	Visit #1*	Visit #2-6	Visit #7
Procedure	Screening and Pretreatment Procedures	Treatment Visit(s) #1 (required) #2-5 (optional) (2 – 10 Weeks Apart)	Follow Up 60 Days Post Last Tx (+/- 30 Days)
Medical History	X		
Pregnancy Verification	X		
Informed Consent	X		
Photographs	X	X	X
Treatment		X	
Treatment Discomfort/ Pain Evaluation		X	
Subject Questionnaires			X
Investigator Questionnaire			X
Adverse Events Assessment		X	X

^{*}Screening and Pretreatment Procedures may occur at the same time as the first Treatment Visit.

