2.15 Statistical Analysis

2.15.1 Hypothesis

For this study to be considered a success, parameters are developed, and the side effect profile is acceptable to the Physician as it relates to this type of treatment.

For secondary objectives to be considered a success, the results from any assessments will need to be statistically significant or have $\geq 80\%$ response rate. In cases where the subject's improvement is being graded on a scale, such as the GAIS scale, we will test the statistical significance of our results against a hypothetical population that would have no change (average score of 4).

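### Section 2.15.5 analyses the CGAIS as a change from a pre-treatment grade that is neither scheduled nor meaningful on that scale, and conflicts with the test against 4 in 2.15.1

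*Combined protocol and SAP*

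**What the plan says.** Section 2.15.5 sets the endpoint: "The primary efficacy variable is the change from baseline to visit 7 (60 days post last treatment, +/- 30 days"), as graded by the physician on the CGAIS. It continues: "Baseline is defined as the last assessment prior to the first treatment". It asks for separate summaries of the observed grade and of its change, fits a repeated-measures model, and adds: "The statistical significance of the mean change from baseline for each treatment group will be determined using a student's paired t-test". For the comparison at Visit 7, significance "will be declared if the two-sided p-value is < 0.05".

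Section 2.13 describes the scale, which "will be used to judge the improvement as seen by the treating Investigator". It has five grades, from 1 (very much improved) to 5 (worse), with 4 meaning no change. Grades 2 to 5 each name the subject's initial or original condition as the reference.

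In the table in section 2.12, the row "Investigator Questionnaire" is marked only under Visit 7. The follow-up text in section 2.9 agrees on timing but words it as optional: "Subject and Investigator questionnaires may be performed at these visits".

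For graded improvement scales such as this one, section 2.15.1 says: "we will test the statistical significance of our results against a hypothetical population that would have no change (average score of 4").

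Photographs before the first treatment are mandatory (2.6), are standardised so that visits can be compared (13.0), and serve the assessment of safety and efficacy (2.13).

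**The concern.** A change score needs two measurements on the same scale. The plan provides one. The missing measurement cannot be supplied by adding a visit, because a scale that rates improvement has nothing to rate before treatment.

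Two sections therefore describe different quantities for the same instrument: a difference between two grades in 2.15.5, and the grade itself compared with 4 in 2.15.1. A programmer who follows 2.15.5 has no input for the change summaries, the paired t-test or the model of change. Someone would have to improvise after the data are in, on the variable that this section calls primary.

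A second, smaller gap concerns how the grade is produced. Its meaning depends on a comparison with the pre-treatment appearance. The protocol text does not say that the treating investigator makes that comparison with the baseline photographs in view, although they will exist for every treated subject.

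**Working it through.** **Is there a baseline grade?** I take the questionnaire row in 2.12 to be the physician questionnaire of 2.13 that carries the CGAIS; the documents show no other investigator instrument.

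| Source | Visit 1 | Treatment visits | Visit 7 |
|---|---|---|---|
| 2.12, investigator's questionnaire | no | no | yes |
| 2.9, follow-up text | – | – | may be performed |
| 2.15.5, needs a CGAIS value | yes (baseline) | – | yes |

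Write Y for the Visit 7 grade and B for the pre-treatment grade. Section 2.15.5 analyses D = Y − B. B is scheduled for 0 of the 20 subjects in 2.15.2, so D can be computed for 0 of 20. Section 2.15.5 has an exclusion rule for subjects with no post-baseline grade, but none for subjects with no baseline grade, so it presumes that B is measured.

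**How does this relate to 2.15.1?** If every B were set to 4, then D = Y − 4, the mean of D is the mean of Y minus 4, and the standard deviation is unchanged. The paired t-test is then exactly the one-sample test against 4. As a check on 20 made-up grades (two 1s, seven 2s, eight 3s, three 4s):

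- mean = (2 + 14 + 24 + 12) / 20 = 52 / 20 = 2.6
- variance = (150 − 52² / 20) / 19 = 14.8 / 19 = 0.779, so SD = 0.883
- t = (2.6 − 4) / (0.883 / √20) = −7.094 on 19 df

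The paired test with B = 4 gives the same t and df. These grades are not a forecast; they show only that a baseline fixed at 4 adds no information. No section tells the analyst to fix it at 4.

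**How long after first treatment is the grade given?** Inputs are 1 to 5 treatments per area, 2 to 10 weeks apart (2.7), and follow-up 30 to 90 days after the last treatment (2.1, 2.9).

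The plan's own durations come first. Section 1.3 gives 3 + 15 + 3 = 21 months in total, which is consistent. The 15 months of participation cannot be rebuilt, because no gap from screening to first treatment is stated. Assuming that gap is also 10 weeks gives 5 × 70 + 90 = 440 days, or 14.5 months, which fits.

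Interval = (number of treatments − 1) × spacing + follow-up window:

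| Treatments | Shortest (days) | Longest (days) |
|---|---|---|
| 1 | 0 + 30 = 30 | 0 + 90 = 90 |
| 3 | 2 × 14 + 30 = 58 | 2 × 70 + 90 = 230 |
| 5 | 4 × 14 + 30 = 86 | 4 × 70 + 90 = 370 |

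The maximum of 370 days is about 12.2 months. With the nominal 60-day follow-up it is 4 × 70 + 60 = 340 days. These are extremes; treatments 2 to 5 are optional.

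**The case against.** The best defence is that 2.15.5 is loosely worded rather than unworkable. On this reading the grade is itself the change, 2.15.1 supplies 4 as the null value, and the paired and one-sample tests then coincide. Study success in 2.15.1 rests on developing parameters and on an acceptable side-effect profile, not on the CGAIS.

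Much of this stands. The Visit 7 grades can be analysed and no data are lost, so a reader who inferred that the trial will have no investigator efficacy data would be going too far. But the loose reading does not fit the text. Section 2.15.5 defines baseline as an assessment made before treatment, and asks for the observed value and the change as two separate summaries.

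A reader might also infer that the grade has no stated reference. That is not so: the scale's own descriptions name the initial or original condition.

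Nor do the documents show that grading is done from memory, that it leans toward crediting improvement, or that the spread from 30 to 370 days measures a recall error. Photographs are to be used for efficacy, subjects may be seen several times in between, and the case report form (Attachment V), which is not among the material read here, may carry a grading instruction. What can be said is that the protocol text leaves the link between the grade and the photographs unstated.

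**Conclusion.** The analysis of the CGAIS in 2.15.5 is wrong as written. It needs a pre-treatment grade that is scheduled for 0 of 20 subjects and that the scale could not provide, and it contradicts 2.15.1. The defect lies in the specification, not in the data to be collected, so it should be corrected before analysis but does not threaten the trial.

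The missing link to the photographs is a secondary gap. The grade may come up to 370 days after first treatment, with a minimum of 30, and the text does not require the baseline photograph to be in view. No size of bias can be derived from this.

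The conclusion rests on the investigator's questionnaire being the CGAIS form, and on the schedule in 2.12 being complete; 2.9 supports both.

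One neighbouring matter is not settled here. Section 1.2 makes blinded photographic evaluation the primary efficacy objective and investigator questionnaires secondary, and the test against 4 in 2.15.1 is stated for secondary objectives. The sponsor must decide separately whether the CGAIS is primary. The correction below is needed either way.

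**What to change.** In 2.15.5, for the CGAIS, delete the baseline definition, the change-from-baseline definition and the change summaries. Replace the repeated-measures model and the paired t-test with a one-sample analysis of the Visit 7 grade against 4, in line with 2.15.1, and name the test. Deleting the definitions alone would leave both methods without input.

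In 2.13, require each treated area to be graded at Visit 7 beside its own photograph from before the first treatment, and record on the CRF that this was done. If a subject contributes several areas, state how they are reduced to one value per subject, since a one-sample test assumes independent values. Align 2.9 with 2.12 on whether the questionnaire is required.

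The cost is wording in these sections, one CRF entry and a little more time at Visit 7; no new visit, rater or subject is needed. One practical check remains. Section 2.6 asks hair-removal subjects to grow hair for at least 5 to 7 days before the baseline photographs, and nothing comparable is stated for Visit 7. The sponsor should confirm that the paired photographs will be comparable for that indication.

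### Section 2.15.5 plans a Visit 13 mixed model and a treatment-group comparison that this one-device, seven-visit study cannot supply; the Visit 7 test against no change in 2.15.1 is still usable and should replace them

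*Combined protocol and SAP*

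**What the plan says.** **Efficacy (2.15.5).** The primary efficacy variable is change from baseline to Visit 7 on the physician-graded CGAIS, with baseline fixed by this rule: "Baseline is defined as the last assessment prior to the first treatment". The model, however, is aimed at another visit: "The change from baseline to visit 13 will be analyzed using a Mixed Model Repeated Measures Analysis of Variance". From that model, "A pairwise treatment group comparison at visit 7 will be performed using the results of this analysis", and "significance with respect to the treatment group comparison at visit 7 will be declared if the two-sided p-value is < 0.05". Satisfaction is placed at two further visits: "Subject satisfaction results from Visits 12 and 13 will also be included in the summary". A within-group test follows: "The statistical significance of the mean change from baseline for each treatment group will be determined using a student's paired t-test".

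**Populations (2.15.3).** One sentence counts all who start: "Everyone who begins the treatment is part of the study whether he or she completes the study or not". A later one restricts the set: "The analysis of demographic, medical history, and efficacy variables will be based on all patients who are randomized and receive at least one treatment". The safety set carries the same restriction and adds a requirement for some safety data.

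**Other analyses.** Section 2.15.4 compares treatment groups on demographic and medical history variables. Section 2.15.6 summarises safety by treatment group, without testing.

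**Design.** Section 2.2 describes an open-label, single-center study of one device. Section 2.5 issues subject numbers in order of entry. Section 2.12 has Visit 1 for screening, Visits 2-6 for treatment and Visit 7 for follow-up, with both questionnaires at Visit 7 only.

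**Success criteria (2.15.1).** Overall success rests on parameters being developed and on an acceptable side-effect profile. Secondary success needs statistical significance or a response rate of at least 80%. Graded scales such as the GAIS are tested against a no-change score of 4.

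**The concern.** The efficacy section names visits, groups and a model that the design does not contain, and its one explicit p < 0.05 rule for efficacy belongs to a comparison that does not exist. An analyst following the text could not produce that result and would have to choose a substitute. Because the study is open label, a substitute chosen late could be chosen with the scores in view.

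The status of the endpoint is also unsettled. Section 2.15.5 makes investigator-rated CGAIS the primary efficacy variable. Section 1.2 lists investigator questionnaires under secondary objectives. Section 3.2 says that investigator assessment of improvement, if collected, is not listed as an objective. These three statements cannot all stand.

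**Working it through.** **1. Visits.** From 2.12: 1 screening + up to 5 treatment + 1 follow-up = 7. Visit 13 is 13 - 7 = 6 beyond the last scheduled visit, and Visit 12 is 5 beyond it. Section 2.15.5 also disagrees with itself, since its own primary variable is at Visit 7.

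**2. Groups.** With g groups there are g(g - 1)/2 pairwise comparisons. One device and no defined subgroup gives g = 1, hence 0 comparisons. The number randomized is 0 of the planned 20.

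**3. Does reading 13 as 7 repair the model?** No. CGAIS (2.13) runs from 1, very much improved, to 5, worse, with 4 meaning no change from the original condition. It already measures change. Section 2.12 schedules 0 ratings before treatment and 1 after, so there is no baseline score to subtract and no scheduled repeated measure for a mixed model.

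**4. What the paired t-test can mean.** For subject i with Visit 7 score Y_i, the paired difference is Y_i - B_i. No B_i is collected. If B_i is set to 4 for everyone, the difference is Y_i - 4 and the paired t-test is identical to a one-sample t-test of Y against 4. That is the reference value in 2.15.1. Section 2.15.1 names no test, and 2.15.5 names the test without the value 4; the two have to be joined explicitly.

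**5. How the significance route compares with the 80% route (illustrative scores, n = 20).** Suppose k subjects score 3 and 20 - k score 4. Then mean difference = -k/20, variance = (k/20)(1 - k/20)(20/19), and t = mean / sqrt(variance/20) on 19 degrees of freedom.

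- k = 3: mean -0.15, variance 0.1342, t = -0.15/0.0819 = -1.83, p = 0.083.
- k = 4: mean -0.20, variance 0.1684, t = -0.20/0.0918 = -2.18, p = 0.042.

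If grade 3 counts as improved, k = 4 is a 20% response, with an exact 95% CI of 5.7% to 43.7%. At the 80% line, 16/20 has an exact 95% CI of 56.3% to 94.3%. The significance route can therefore be met far below the response route.

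**6. Why the test must be named.** For the same k = 4 scores, an exact signed-rank test uses only the four non-zero differences, and p = 2 x (1/2)^4 = 0.125. The t-test is significant and the signed-rank test is not.

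The plan gives no power, effect size or SD for N = 20 (2.15.2), so there is no planned figure to reproduce.

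**The case against.** The best defence is that these are drafting leftovers with limited reach. Much of that stands.

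- **A reader might infer that study success cannot be determined.** The documents do not support this. Overall success in 2.15.1 does not use the group comparison. The secondary criterion for graded scales tests against a score of 4, which needs no groups, no Visit 13 and no pre-treatment rating.
- **A reader might infer that no efficacy analysis is possible.** Visit 7 descriptive summaries and the test against 4 remain feasible. What fails is the mixed model, the pairwise comparison with its significance rule, and the Visit 12 and 13 summary.
- **A reader might infer that the analysis sets are simply empty.** That follows only if the restriction to randomized patients is read alone. Section 2.15.3 also counts everyone who begins treatment, so the defect is an internal conflict.
- **A reader might infer that all of 2.15.3 to 2.15.6 assumes 13 visits.** Visits beyond 7 appear only in 2.15.5. The other sections carry only the randomization or group wording.
- **Late rewriting is not inevitable.** Section 21.0 allows a formal amendment, which could be made before the scores are reviewed.

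Treatment group might also mean indication: 2.15.5 mentions the indication being treated, and 1.1 and 3.3 list several. No section says so. Section 2.1 allows several treated areas per subject, so such groups need not be independent. The possibility does justify keeping summaries by indication. Follow-up for each area (2.1) and unscheduled visits (2.10) may add contacts, but neither creates a numbered Visit 12 or 13.

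**Conclusion.** The point holds in bounded form. As written, the mixed model to Visit 13, the treatment-group comparison that carries the only stated efficacy significance rule, and the satisfaction summary at Visits 12 and 13 cannot be carried out. Correcting the visit number alone would not make the model workable. The paired t-test works only with baseline set to 4, which 2.15.5 does not say. The population wording conflicts with itself, and the status of CGAIS conflicts across 1.2, 2.15.5 and 3.2.

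The visit, group and rating counts come directly from the documents and need no assumption. The p-values and intervals are illustrations: they assume 20 rated subjects, one score each, and the score patterns shown. They show why the test and the meaning of response should be fixed in advance; they do not predict the result.

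**What to change.** 1. **2.15.3:** remove the randomization condition. The efficacy and demographic set is every subject who received at least one treatment. The safety set is those of them who also have some safety data.
2. **2.15.4 and 2.15.5:** delete the between-group tests, the mixed model and the pairwise comparison, and move the satisfaction summary to Visit 7. In 2.15.4 to 2.15.6, summarise overall and, where wanted, by indication in place of treatment group.
3. **2.15.5, test:** compare the Visit 7 CGAIS score with 4 (no change, as in 2.15.1) by a two-sided one-sample t-test at 0.05, with one value per subject. If several areas are rated, fix the rule for choosing or combining them before any data review.
4. **2.15.5, reporting:** give the proportion improved with an exact 95% CI beside the p-value. The sponsor should state in advance which grades count as response for the 80% criterion. Whether grade 3 counts is the sponsor's decision; 2.13 describes it as obvious improvement with re-treatment indicated.
5. **Status of CGAIS:** reconcile 1.2, 2.15.5 and 3.2. If CGAIS becomes secondary, reword the 2.15.5 exclusion rule for subjects with no post-baseline assessment so that it refers to CGAIS and not to the primary efficacy variable.

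The cost is text edits to 2.15.3 to 2.15.6 and to the objective wording in 1.2 or 3.2, and at most one CRF field if the per-subject rule designates an area. No new subjects, visits or assessments are needed. The analysis of the blinded photographs, and the wording in 2.9 that makes the questionnaires optional, are separate points that these edits do not settle.
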